- An additional hemoglobin must be checked 3 to 6 hours after the initiation of the first (Priming) and second (Week 2) doses of Hu5F9-G4 (magrolimab). The patient should be transfused as clinically appropriate. Investigators should consider additional hemoglobin monitoring during the first week of treatment in patients with symptoms of anemia or at increased risk of complications of anemia.

Men and women of reproductive potential must use effective contraception while receiving study treatment and for 4 months after the last dose of Hu5F9-G4 (magrolimab). Male patients whose partners are pregnant may continue study treatment and should use barrier method contraception (condom) to prevent exposing the fetus. Refer to Section 6.8 of for further details.

Since infusion reactions can occur, all patients should be monitored pre-priming dose (within 30 minutes), every 30 minutes (±10) during priming dose infusion, for 1-hour post-infusion of the priming dose with vital signs (heart rate, respiratory rate, blood pressure, temperature, pulse oximetry) or as clinically indicated. Vital signs and AEs will be collected 30 (±10) minutes and 1 hour (±10 minutes) post-infusion. Patients who experience any treatment-related adverse events during the observation period should be further monitored as clinically appropriate (e.g., for up to 24 hours post-dose). All patients should be monitored with hourly (±20 minutes) vital signs during and for 1-hour (±20 minutes) post-infusion for Cycle 1. Further doses (Cycle 2+) do not require post-infusion observation, but hourly (±20 minutes) vital signs during the infusion. Patients who experience any treatment-related AEs during the observation period should be further monitored as clinically appropriate.

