# **Hematologic Toxicity:**

- Anemia is an expected toxicity of Hu5F9-G4 (magrolimab) and dinutuximab, especially in patients who have had extensive prior therapy with chemotherapy, and therefore anemia and a need for blood transfusions will not be considered a DLT. Grade 3 hemolytic anemia that is medically significant, requires hospitalization or prolongation of existing hospitalization, is disabling, or limits self-care activities of daily life (ADLs) will be considered a DLT.
- Thrombocytopenia can be expected in this heavily pretreated population who have had extensive prior therapy with chemotherapy, and therefore platelet count decreased in the absence of hemorrhage will not be considered a DLT unless < 25,000/mcL for > 14 days despite supportive care.
- Grade 3 or 4 lymphopenia or leukopenia not associated with other clinically significant consequences.

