#### Non-hematological Toxicity:

- Any Grade 3 or greater, non-hematological toxicity will be considered a DLT with the following *exceptions*:
  - a. Pain and sensory neuropathy are expected toxicities of dinutuximab, but pain or sensory neuropathy at levels described in Table 8: Adverse Reactions Requiring Permanent Discontinuation of Dinutuximab will be considered a DLT. Pain requiring sedation and respiratory support for control will also be considered a DLT.
  - b. Tumor lysis syndrome, including associated abnormalities (e.g., electrolytes, uric acid, renal function).
  - c. Grade 3 low electrolyte levels that are correctable and asymptomatic.
  - d. Grade 3 hypoalbuminemia. Such individuals should receive supplementation as indicated. Hypocalcemia toxicity grade should be assigned based on the calcium level corrected for degree of hypoalbuminemia according to the following formula: for every albumin decrease of 1 gm/dL a total calcium increase of 0.2 mmol/L is to be made.
  - e. Grade 3 transaminase, alkaline phosphatase, bilirubin or other liver function test elevation, provided there is resolution to  $\leq$  grade 2 with supportive care within 7 days and is not associated with other clinically

significant consequences. Grade 3 transaminase elevation, alkaline phosphatase or hyperbilirubinemia elevation of any duration in patients with liver involvement due to tumor will not be considered a DLT, although Grade 4 hepatic toxicity will be considered DLT.

- f. Transient Grade 3 nausea, vomiting, diarrhea, local reactions, influenza-like symptoms, myalgias, fever, headache, acute pain, or skin toxicity that resolves to ≤Grade 2 within ≤72 hours after medical management (e.g., supportive care, including immunosuppressant treatment) has been initiated.
- g. Grade 3 fatigue that resolves to ≤Grade 2 within 1 week.
- h. Grade 3 infusion reactions in the absence of an optimal pretreatment regimen, which is defined as acetaminophen or a comparable non-steroidal anti-inflammatory agent, plus an antihistamine and corticosteroids.
- i. Grade 3 or 4 infection or neutropenic fever although Grade 4 infection uncontrolled for > 7 days will be considered DLT.
- j. Grade 3 electrolyte disturbances (hyperkalemia, hypophosphatemia, hyperuricemia, etc.) that resolves to ≤Grade 2 or baseline within 1 week. Grade 4 hyponatremia not responsive to appropriate fluid management for dinutuximab will be considered a DLT.

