- k. Other single laboratory values out of normal range that have no clinical correlate and resolve to Grade ≤1 or to baseline within 7 days with adequate medical management.
- 1. Tumor flare phenomenon defined as local pain, irritation, or rash localized at sites of known or suspected tumor.
- m. Grade 3 decrease in vision that resolves to grade 1 or better before the next dose dinutuximab will not be considered a DLT and dose will be modified as per Section 7.3.2. Eye disorders such as sluggish light reflex or other visual disturbances that do not cause visual loss will not be considered DLT. Subtotal or total vision loss will be considered a DLT.
- n. Capillary leak syndrome and/or hypotension (grade 3-4) which resolves to ≤Grade 2 or baseline within 8 hours with maximum supportive care.

Management and dose modifications associated with the above adverse events are outlined in Section 7.

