# 7.1 Dosage modification for Hu5F9-G4 (magrolimab)

Nausea	Management/Next Dose for Hu5F9-G4 (magrolimab)	
≤ Grade 1	No change in dose	
Grade 2	Hold until ≤ Grade 1. Resume at same dose level.	
Grade 3	Hold until < Grade 2. Resume at one dose level lower, if indicated.*	
Grade 4	Off protocol therapy	
*Patients requiring a delay of >2 weeks should go off protocol therapy.		
Recommended managen	nent: antiemetics	

Vomiting	Management/Next Dose for Hu5F9-G4 (magrolimab)	
≤ Grade 1	No change in dose	
Grade 2	Hold until ≤ Grade 1. Resume at same dose level.	
Grade 3	Hold until < Grade 2. Resume at one dose level lower, if indicated.*	
Grade 4	Off protocol therapy	
*Patients requiring a de	lay of >2 weeks should go off protocol therapy.	
Recommended manage	ement: antiemetics	

Diarrhea	Management/Next Dose for Hu5F9-G4 (magrolimab)
≤ Grade 1	No change in dose
Grade 2	Hold until ≤ Grade 1. Resume at same dose level.
Grade 3	Hold until < Grade 2. Resume at one dose level lower, if indicated.*
Grade 4	Off protocol therapy
*Patients requiring	g a delay of >2 weeks should go off protocol therapy.

Recommended management: Loperamide antidiarrheal therapy with dosage schedule: 4 mg at first onset, followed by 2 mg with each loose motion until diarrhea-free for 12 hours (maximum dosage: 16 mg/24 hours)

Adjunct anti-diarrheal therapy is permitted and should be recorded when used.

Neutropenia	Management/Next Dose for Hu5F9-G4 (magrolimab)	
≤ Grade 1	No change in dose	
Grade 2	No change in dose.	
Grade 3	No change in dose.	
Grade 4 Hold until $\leq$ Grade 2. Resume at same dose level.*		
*Patients requiring a de	lay of >2 weeks should go off protocol therapy.	

Thrombocytopenia Management/Next Dose for Hu5F9-G4 (magrolimab)		
≤ Grade 1	de 1 No change in dose	
Grade 2	No change in dose.	
Grade 3 Hold until ≤ Grade 2. Resume at same dose level. *		
Grade 4 Hold until ≤ Grade 2. Resume at one dose level lower, if indicated. *		
*Patients requiring a del	ay of >2 weeks should go off protocol therapy.	

Anemia	Management/Next Dose for Hu5F9-G4 (magrolimab)
≤ Grade 1	No change in dose
Grade 2	No change in dose
Grade 3 hemolytic anemia that is	

Anemia	Management/Next Dose for Hu5F9-G4 (magrolimab)
	First occurrence: Reduce by 1 dose level.  • If recurs after 1 dose level reduction: permanently discontinue unless patient is clinically benefitting.
Grade 4	First occurrence: permanently discontinue unless patient is clinically benefitting.

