		Week 1	Week 2		Weeks 3-4	Week 1		Weeks 2-3 	Therapy	Safety	Follow Up 	
Scheduling Window	Within 28 days	Day 1	Day 1 ±2 days	Day 2-5 ±2 days	Day 1 ±2 days	Day 1 ±2 days	Day 2-5 ±2 days	Day 1 ±2 days	Within 10 days after last IP dose	30 days after last IP dose ±7 days	Month 2, 4, 6, 9, 12 and annually (Year 2-5)	
Administrative Procedures												
Informed consent/assent	X											
Eligibility evaluation	X											
Medical history 	X	X	X	X	X	X	X	X	X	X	X	
Concomitant medications 	X	X	X	X	X	X	X	X	X	X	X	
Treatment												
Hu5F9-G4 (magrolimab) administration 		X	X		X	X		$X^{20}$				
Dinutuximab administration 				X			X					
Clinical Assessments												
Height, weight 	X	X	X			X			X	X	X	
Physical exam 	X	X	X			X			X	X	X	
Vital signs 	X	X	X	X	X	X	X	X	X	X	X	
ECG	X											
ECHO, MUGA or Cardiac MRI	X											
Performance status 	X	X	X			X				X	X	
Disease evaluation 	X	_	End of Cycle 2 and 4, and then after every 4 cycles								X	
Confirmatory imaging 				-	As į	per Section I	Error! Refere	ence source not	found.			
Bone marrow aspiration and biopsy if NBL/ganglioneuroblastoma 10, 21	X									X		
AE and SAE evaluation 							Continuo	ısly			1	
Clinical Laboratory Tests 												

Version Date: 02/02/2024

THIS PROTOCOL IS FOR RESEARCH PURPOSES ONLY, SEE PAGE 1 FOR USAGE POLICY

Treatment Cycles/Visits	Screening				Follow Up						
		Priming	Cycle 1			Cycle 2 and subsequent cycles			End of	G C .	E II II 17
		Week 1	Week 2		Weeks 3-4	Week 1		Weeks 2-3 	Therapy	Safety	Follow Up 
Scheduling Window	Within 28 days	Day 1	Day 1 ±2 days	Day 2-5 ±2 days	Day 1 ±2 days	Day 1 ±2 days	Day 2-5 ±2 days	Day 1 ±2 days	Within 10 days after last IP dose	30 days after last IP dose ±7 days	Month 2, 4, 6, 9 12 and annually (Year 2-5)
Pregnancy test 	X	As required locally									
CBC with differential and platelets	X	$X^{22}$	X 			X				X	
Electrolytes, creatinine, urea (BUN), Ca 2+ , PO 4  , Mg 2+	X	X	X			X				X	
ALT, AST, bilirubin	X	X	X			X				X	
Amylase, lipase, CRP	X	X	X			X					
Blood cell ABO phenotyping (minor antigens) 	X→										
Type and screen (ABO/rhesus) 	X	X→									
Direct Antiglobulin Test (DAT) [direct Coombs test]	X	>									
Urinalysis	X										

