- Confirmatory scans should also be performed according to Section 12 in patients with measurable disease. The same method of assessment and technique should be used throughout the study.
- All AEs occurring within 30 days after the last dose of the study drug must be reported in a routine manner using Rave. Additionally, all AEs that occur within 30 days after the last dose of the study drug, regardless of causality, meeting the expedited reporting criteria outlined in Section 10.3 must also be reported expeditiously via CTEP-AERS.
- All clinical laboratory tests must be performed in a licensed laboratory according to local policy. Pregnancy tests may be performed at the site using a licensed test. Laboratory results outside the limits of eligibility may be repeated to confirm eligibility and must be within the limits of eligibility before treatment initiation. Clinical laboratory tests conducted during screening do not need to be repeated on C1D1 if completed within 7 days prior to treatment initiation. All clinical laboratory tests during the treatment period must be performed within 72 hours prior to dosing. If treatment is delayed all clinical laboratory tests (and their respective windows) will adjust with the dose delay to reflect the patient's clinical status at the time of dosing.
- Females of childbearing potential must have a negative urine or serum pregnancy test within 72 hours prior to treatment initiation. Additional pregnancy tests (serum or urine) should be obtained throughout the study in accordance with local policy.
- Specimen **must** be drawn, completed, resulted and active per institutional guidelines prior to the Priming dose of Hu5F9-G4 (magrolimab). ABO, Rh, and DAT may be pan-reactive due to Hu5F9-G4 (magrolimab) binding to red cells (see Section 7.2.4).
- Upon treatment discontinuation, patients will complete the Safety Visit within 30 (±7) days, and Follow-up Visits at month 2 (± 1 week), month 4 (± 2 weeks), month 6 (± 4 weeks), month 9 (± 4 weeks), and month 12 (± 2 months) and then yearly (± 2 months) until year 5, or until disease progression or until death, lost to follow-up, withdrawal of consent, or the end of the study, whichever occurs first. If a subsequent anti-cancer therapy is to be administered after treatment discontinuation but before the scheduled Safety Visit, the Safety Visit assessments should be conducted prior to the start of the new therapy if possible.

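### The Arm B calendar marks no blood panel before four of the six full magrolimab doses in Cycles 1-2, although Section 7.1 ties the next dose to platelet and neutrophil grade

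*Combined protocol and SAP*

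**What the plan says.** **Calendar (Section 11, Arm B).** Three rows carry the same marks: "CBC with differential and platelets", the electrolyte/creatinine/urea row, and the ALT/AST/bilirubin row. All are marked at screening, priming Day 1, Week 2 Day 1 (the first full dose), Day 1 of Cycle 2 and later cycles, and the Safety visit. The cells for the dinutuximab days, for Cycle 1 Weeks 3-4 and for Weeks 2-3 of Cycle 2 onward are blank.

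**Footnote to the laboratory block.** "All clinical laboratory tests during the treatment period must be performed within 72 hours prior to dosing". The next sentence moves the tests and their windows along with any dose delay.

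**Dose holds (Section 7.1).** Magrolimab is held for Grade 4 neutropenia and for Grade 3 or 4 thrombocytopenia. The Grade 4 thrombocytopenia rule reads "Hold until ≤ Grade 2. Resume at one dose level lower, if indicated".

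**Laboratory DLTs (Section 6.3).**
- A low platelet count without hemorrhage is not a DLT "unless < 25,000/mcL for > 14 days despite supportive care".
- Item e exempts Grade 3 liver changes that resolve to no worse than "grade 2 with supportive care within 7 days".
- Item j exempts "Grade 3 electrolyte disturbances (hyperkalemia, hypophosphatemia, hyperuricemia, etc.) that resolves to ≤Grade 2 or baseline within 1 week".
- Item k exempts other isolated laboratory values that "resolve to Grade ≤1 or to baseline within 7 days with adequate medical management".

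**Hemoglobin (Section 6.2.1.3).** Minimum levels apply before the first two magrolimab doses, and "An additional hemoglobin must be checked 3 to 6 hours after the initiation of the first (Priming) and second (Week 2) doses".

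**The concern.** The dose-hold rule and the calendar do not match. A site that follows the grid reaches the Week 3 and Week 4 doses of Cycle 1, and the Week 2 and Week 3 doses of Cycle 2, with no marked platelet or neutrophil count on which to apply Section 7.1. These doses can be given to outpatients (Section 6, introduction), so an inpatient stay cannot be relied on to supply the count.

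The same gap touches DLT assessment. Section 6.1.1.2 uses the first three Arm B patients to confirm the RP2D, and Section 6.4 continues DLT monitoring through Cycle 1 of the expansion cohorts. If testing between the marked panels is left to local habit, laboratory DLTs may be found more readily at some sites than at others.

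**Working it through.** The plan gives no figure to reproduce here. The check reads the grid, counts doses and measures intervals.

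**Step 1: read the grid.** Inputs are the Arm B calendar (Section 11) and the dosing schedule (Section 6.2.1.2). The columns can be trusted because, in the same table, the magrolimab row is marked at every weekly dosing column of Cycles 1-2, the dinutuximab row only at Days 2-5, and the vital-signs row throughout. Study days are nominal, with priming as day 1.

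| Visit | Study day | Magrolimab | Research blood | CBC, chemistry, liver |
|---|---|---|---|---|
| Priming | 1 | 1 mg/kg | marked | marked |
| Cycle 1, Week 2 Day 1 | 8 | full | marked | marked |
| Cycle 1, Week 3 Day 1 | 15 | full | marked | blank |
| Cycle 1, Week 4 Day 1 | 22 | full | marked | blank |
| Cycle 2, Week 1 Day 1 | 29 | full | marked | marked |
| Cycle 2, Week 2 Day 1 | 36 | full | marked | blank |
| Cycle 2, Week 3 Day 1 | 43 | full | marked | blank |

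**Step 2: count doses.** Full doses in Cycles 1-2: 3 + 3 = 6. Doses with a marked panel: 2. Doses without: 6 - 2 = 4.

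**Step 3: measure the interval between marked panels.**
- Nominal: 29 - 8 = 21 days.
- With the 72-hour draw window: shortest (29 - 3) - 8 = 18 days; longest 29 - (8 - 3) = 24 days.
- Adding the ±2-day window at each visit: 18 - 4 = 14 days to 24 + 4 = 28 days.

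**Step 4: place the next panel against the DLT window.** With the 72-hour window, the panel before Cycle 2 falls on study days 26-29, which are Cycle 1 days 26 - 7 = 19 to 29 - 7 = 22. That is at or just past the end of the 21-day window. A panel on Day 1 and one then cannot by themselves show whether a change lasted more than 7 or more than 14 days.

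**Step 5: look for another source of required values.** The hemoglobin check covers only the priming and Week 2 doses and gives no platelets, neutrophils or chemistry. Section 7 promises tests at regular intervals but sets none. Section 7.2.3 refers back to the schedule of assessments for CBCs and chemistries.

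**Step 6: read the footnote both ways.** If it is a window for marked visits, the four doses have no required count. If it covers every dose, the grid is wrong at those four doses, and read literally it would also require panels before each dinutuximab day. Both readings need a text change.

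**The case against.** The strongest defence joins the footnote to Section 7.1. The footnote speaks of all laboratory tests before dosing, its stated purpose is to reflect the patient's condition when the drug is given, and Section 7.1 cannot be applied without a count. On that view a pre-dose count is already required. The reading is fair, and it rules out a flat statement that the protocol requires none. It does not remove the conflict with the grid, and the footnote's own reference to windows fits the narrower reading as well.

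Second, the dinutuximab rules on blood products, creatinine and sodium (Sections 7.3.2.1, 7.3.2.4, 7.3.2.5) imply serial inpatient testing. That stands for Days 2-5. It does not reach the Week 3-4 doses.

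Third, a reader might infer that abnormal values need never be repeated. The documents do not support that. A hold until Grade 2 or better, with removal from therapy after a delay of more than 2 weeks, presupposes repeat counts, and Section 7.3.2.4 has a Day 7 creatinine judgement. What is missing is a stated frequency, chiefly for liver tests.

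Fourth, AEs are evaluated at every visit (Section 7), safety data are monitored in real time (Section 6.4), and the study chair's DLT evaluations are reviewed weekly (Section 13.1.2). None of these creates a test, but they limit uneven ascertainment.

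Finally, a reader might infer that many laboratory DLTs would go unseen. With panels only on Cycle 1 days 1 and 22, no local testing, and onset equally likely on days 2-21, an 8-day liver event is missed for 13 of 20 onset days, a 14-day event for 7 of 20 and a 21-day event for none. The answer follows from the assumed duration. No document supports uniform onset, and the inpatient rules count against an absence of testing. These figures are not evidence of harm.

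**Conclusion.** The inconsistency is real and should be corrected. The Arm B grid marks no panel before 4 of the 6 full magrolimab doses in Cycles 1-2, with a nominal 21 days between marked panels (14-28 with visit and draw windows). Section 7.1 needs platelet and neutrophil grades at those doses.

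The practical consequence is dosing safety first and evenness of laboratory DLT ascertainment second. A reader might go further and infer that the RP2D is unsound. The documents do not support this: the dose is chosen in Arm A, 21 days must pass after Cycle 1 in the last of the first three Arm B patients before more are treated (Section 6.1.1.2), and 2 DLTs in the first 5 patients, or at least 2 in 6, leads to a discussion (Section 6.4).

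The conclusion rests on the Arm B grid as printed and on no other section scheduling a panel at these doses. It does not assume that sites fail to test. Nothing is concluded about Arm A, whose laboratory marks cannot be placed in their columns in the available text.

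**What to change.** 1. In the Arm B calendar, mark CBC with differential and platelets, electrolytes/creatinine and ALT/AST/bilirubin before the Cycle 1 Week 3-4 and Cycle 2 Week 2-3 magrolimab doses. The last column covers Cycle 2 and later cycles together, so its mark needs a note limiting it to Cycle 2.
2. Reword the footnote to read: *a panel is required within 72 hours before every magrolimab dose in Cycles 1-2 and before Day 1 of each later cycle.*
3. Optionally, state that a Cycle 1 laboratory value that could become a DLT is repeated until it resolves. Weekly panels improve detection but do not by themselves settle a 7-day or 14-day duration. The way DLT duration is counted should stay as it is.

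**Cost.** This is a calendar and footnote amendment. Research blood is already scheduled before each weekly magrolimab dose in Cycles 1-2 (Tables 2 and 3), so no new visit is needed. After a dose delay the two draws may separate, because research samples keep their calendar dates while clinical tests move with the dose. Four added draws at 2-4 mL each (assumption) come to 4 × 2 = 8 to 4 × 4 = 16 mL. For a 12-kg child at 75 mL/kg (assumption, 900 mL), that is 8/900 = 0.9% to 16/900 = 1.8% of blood volume. Any repeats under item 3 would add to this. A few more laboratory AEs may also be recorded.

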# CHILDREN'S ONCOLOGY GROUP

#### PED-CITN-03

THIS PROTOCOL IS FOR RESEARCH PURPOSES ONLY, SEE PAGE 1 FOR USAGE POLICY

- Dinutuximab will be administered on Days 2-5 during the first week of every cycle as specified in Section 6.2. Administer antihistamines, antipyretics (i.e. acetaminophen and ibuprofen) and analgesia prior to each dinutuximab infusion as per Section 6.2.
-  Both height and weight will be recorded at screening. Only weight will be recorded at subsequent applicable visits.
- A complete physical examination as well as a cancer-specific physical exam will be performed at screening. Physical exams at subsequent applicable visits will be targeted based on the investigator's clinical observations and symptomatology. If a physical exam is performed within 3 days prior to a subsequent dosing day it does not need to be repeated on the dosing day provided there is no new status change.
- Vital signs = heart rate, respiratory rate, blood pressure, temperature, pulse oximetry. See Sections 6.2.1.4 for collection timepoints during and after infusion. Vital signs must also be collected at each non-dosing visit.
-  Karnofsky score of ≥50% is required for patients >16 years, and Lansky score of ≥50% is required for patients ≤16 years. Patients unable to walk due to paralysis, but who are using a wheelchair, will be considered ambulatory for the purpose of assessing the performance score. See APPENDIX A.
- Baseline disease evaluation will occur within 28 days of treatment initiation. During the treatment period Cycles 1 through 4, patients in Cohorts B1, B2 and B3 should be re-evaluated for response at the end of Cycles 2 and 4. After Cycle 4, disease evaluation will occur every 12 weeks (after every 4 cycles). Disease evaluations should occur within 7 days prior to dosing of the subsequent cycle. If treatment is delayed, disease evaluations will follow the originally scheduled calendar dates and should not be adjusted for the dose delay. The same method of assessment and technique should be used throughout the study. See Section 12 for disease parameters, methods of assessment, and response criteria. Cohort B4 refer to Section 12 for disease evaluation timepoints. For patients with neuroblastoma/ganglioneuroblastoma, bilateral bone marrow aspirates and trephine biopsies are required at all disease assessment time points (see Section 12.2) and Follow-up Visits for disease evaluation.
- Confirmatory scans should also be performed according to Section 12 in patients with measurable disease. The same method of assessment and technique should be used throughout the study.
- All AEs occurring within 30 days after the last dose of the study drug must be reported in a routine manner using Rave. Additionally, all AEs that occur within 30 days after the last dose of the study drug, regardless of causality, meeting the expedited reporting criteria outlined in Section 10.3 must also be reported expeditiously via CTEP-AERS.
- All clinical laboratory tests must be performed in a licensed laboratory according to local policy. Pregnancy tests may be performed at the site using a licensed test. Laboratory results outside the limits of eligibility may be repeated to confirm eligibility and must be within the limits of eligibility before treatment initiation. Clinical laboratory tests conducted during screening do not need to be repeated on C1D1 if completed within 7 days prior to treatment initiation. All clinical laboratory tests during the treatment period must be performed within 72 hours prior to dosing. If treatment is delayed all clinical laboratory tests (and their respective windows) will adjust with the dose delay to reflect the patient's clinical status at the time of dosing.
- Females of childbearing potential must have a negative urine or serum pregnancy test within 72 hours prior to treatment initiation. Additional pregnancy tests (serum or urine) should be obtained throughout the study in accordance with local policy.
- Specimen **must** be drawn, completed, resulted and active per institutional guidelines prior to the Priming dose of Hu5F9-G4 (magrolimab). ABO, Rh, and DAT may be pan-reactive due to Hu5F9-G4 (magrolimab) binding to red cells (see Section 7.2.4).
- Upon treatment discontinuation, patients will complete the Safety Visit within 30 (±7) days, and Follow-up Visits at month 2 (± 1 week), month 4 (± 2 weeks), month 6 (± 4 weeks), month 9 (± 4 weeks), and month 12 (± 2 months) and then yearly (± 2 months) until year 5, or until disease progression or until death, lost to follow-up, withdrawal of consent, or the end of the study, whichever occurs first. If a subsequent anti-cancer therapy is to be administered after treatment discontinuation but before the scheduled Safety Visit, the Safety Visit assessments should be conducted prior to the start of the new therapy if possible.
  - Follow-up Visits will be completed in-person unless the patient does not agree to continue in-person visits. In this case telephone contact may be arranged to ensure the collection of as many safety and efficacy parameters as possible. A patient that agrees to modified follow-up is not considered to have withdrawn consent or to have withdrawn from the study.

THIS PROTOCOL IS FOR RESEARCH PURPOSES ONLY, SEE PAGE 1 FOR USAGE POLICY

- Patients removed from protocol therapy for unacceptable AE(s) will be followed until resolution or stabilization of the AE. In addition, these patients will complete the EOT, Safety, and Follow-up Visits according to protocol.
- All blood draws for correlative exploratory biology studies will be performed according to the schedule outlined in Table 3, Specimen Collection Schedule; and Section 5. All blood draws for correlative exploratory biology studies must be performed prior to dosing. If treatment is delayed, blood draws for correlative exploratory biology studies will follow the originally scheduled calendar dates and should not be adjusted for the dose delay.
- Archival slides will be requested from all patients. If available, clinical biopsies or surgical samples obtained during treatment or at disease progression will be requested. Cohort B4 Pulmonary metastases resected from staged resection at enrollment and then after one cycle of protocol therapy OR if only one resection performed, tissue will be requested at enrollment after surgical metastasectomy.
-  After Cycle 2, Hu5F9-G4 (magrolimab) will be administered ONLY on Day 1 of week 1 and week 3 (week 2 will be a week of rest).
- Bone marrow aspirations will be conducted in all patients with neuroblastoma (as per INRC). Week 1, Day 1 collection is mandatory, *except* if viably frozen bone marrow aspirate collected within 4 weeks (28 days) of the Priming Dose (Week 1, Day 1) is available and can be provided to the EET Biobank. Bone marrow aspirates are required at all disease assessment timepoints (end of Cycle 2, 4, 8 and 12). Bone marrow aspirate at End of Therapy is optional.
- Within 24 hours prior to the Priming dose (Week 1) of Hu5F9-G4, hemoglobin must be ≥ 9.5 g/dL. Within 24 hours prior to the first full dose (Week 2) of Hu5F9-G4, hemoglobin must be ≥ 9.0 g/dL (see Section 6.2.1.3). Hemoglobin must be checked 3 to 6 hours after the initiation of the first and second doses of Hu5F9-G4 (magrolimab).

